5. INTRODUCTION

There are 15 million [Ref. 1] interventional, catheter based procedures performed annually. The rapid development of percutaneous 'minimal invasive therapy' and the increase of the aging population of which this therapy is apposite, has led to the need for instrumentation to minimise the risk of complications associated with closing the access site, post procedure. At the end of these procedures the arterial puncture must be closed in order to achieve haemostasis and restore the continuity and function of the artery through which the intra-vascular access was gained.

Examples of currently emerging percutaneous endovascular procedures include:

- Aortic Valve Replacement
- Mitral Valve Repair
- Abdominal Aneurysm Repair
- Thoracic Aneurysm Repair
- Tricuspid Valve Replacement

These procedures require larger size access sites ranging from 12 to 24 F. Currently, these large access sites are routinely closed via surgical access and sutured repair, performed in an operating theatre whilst patients are typically under general anaesthetic. In order to provide a less invasive percutaneous, safe, secure and simple mechanical closure of these large arteriotomies and shorten the time taken to perform these closures, Vivasure is developing a new large hole percutaneous vascular closure device named VIVASURE CLOSURE DEVICE, also known as

PerQseal[®], Figure 1, to induce arterial haemostasis in patients undergoing transfemoral endovascular procedures.

[figure not shown]

Figure 1. Pictorial image of Delivery System showing the various components.

5.1 Implant

The implant, Figure 2, has three components; the foot-core (scaffold), flexible-wing (patch) and extraarterial-pin (locator). The foot-core is attached to the flexible-wing at its base and has a neck inclined at an angle (30°) from the base. *In situ* the foot-core neck is mostly extraarterial. The foot-core also acts as a scaffold to secure the flexible-wing against the vessel inner wall.

[figure not shown]

Figure 2. Pictorial image of PerQseal® closure device implant in situ, showing components and end on view of Implant deployed within a sectioned artery.

The flexible-wing of the implant is supplied in the packaging in its relaxed, flat state attached to the shaft of the Delivery System, Figures 4. As the device is removed from the packaging tray the flexible-wing is coiled into a cylindrical shape (via the loading funnel), into the device's loading cannula ready for insertion into the artery. The implant is inserted into the artery through the Introducer-sheath and over a guidewire. The flexible-wing unfolds when exposed in the artery. The implant is designed to be centrally positioned relative to the arteriotomy with the intraarterial

components acting as an internal tamponade. Hemodynamic hydraulic pressure within the artery helps to push the flexible-wing against the luminal surface of the artery and effect a seal. The anterior surface of the wing is coated in a fine mesh of Polydioxanone material designed to entrap circulating erythrocytes, leukocytes and platelets, which help oppose the flexible-wing to the artery wall (surrounding the arteriotomy). These cells are activated via the intrinsic pathway by the exposed collagen of the arteriotomy and become adhered to the collagen by a cross-linked fibrin clot within the arteriotomy and arterial wall surrounding the arteriotomy.

All implant materials are medical grade synthetic absorbables. The materials have been selected to ensure the implant does not cause adverse tissue reaction, haemolysis, severe thrombogenesis or emboli formation. The implant components are manufactured from Polydioxanone (PDO). PDO is commonly used as an absorbable suture material PDS™, (Ethicon), indicated for cardiovascular use, with excellent clinical history for over 30 years [Ref. 2 and 3]. All three components are made from the same Polydioxanone Resomer X 206 S bioabsorbable materials.

The PerQseal[®] closure device implant is designed to achieve a secure and rapid seal of the access site at conclusion of the endovascular procedure, with implant absorption within 180 days.

5.2 Introducer

The PerQseal® Introducer consists of a sheath and dilator with a blood signal port, which accommodates up to a 0.035 in. (0.89 mm) guidewire. The Introducer is supplied in two sizes. The Introducer is designed to allow the operator to easily position the Introducer relative to the arteriotomy for optimum delivery of the implant. Refer to Figure 3, which shows the key features of the Introducer.

[figure not shown]

Figure 3. Pictorial image of Introducer, showing features.

[figure not shown]

Figure 4. Pictorial image of device in tray, as supplied, showing location of various components.

5.3 Delivery System

The PerQseal® closure device delivery system comprises the user interface for the percutaneous delivery of the implant to the arteriotomy and a deployment mechanism. The delivery system has a handle at its proximal end and a flexible shaft, which attaches to the implant at the distal end, Figure 1.

All materials of the delivery system are medical grade polymers, selected for their biocompatibility and functional requirements.

The implant is loaded into the loading cannula upon removal from the protective tray. The delivery system is designed to interface with the supplied Introducer and designed to deliver the implant with minimal movement and to ensure single use of the device.

5.4 Delivery of the Implant

The implant has been designed to be delivered into the artery via a supplied Introducer-sheath and over a 0.014" guidewire. Hence, the delivery sequence starts with the Introducer-sheath and 0.014" guidewire *in situ* (approx. 4 cm) within the vessel.

The loading cannula (containing the implant) is first inserted into the Introducer-sheath hub. This engages the loading cannula with the sheath hub.

The Sheath-cam is rotated (Figure 1), which withdraws the Introducer-sheath, allowing the implant to unfold within the artery. The implant is then positioned against the artery wall closing the arteriotomy. Once tamponade is confirmed the guidewire is removed, the Cam lock depressed, and the Release-cam is rotated to deploy the extraarterial-pin and release the implant. This completes the deployment and seals the arteriotomy.

6. PURPOSE OF THE STATISTICAL ANALYSIS PLAN (SAP)

The purpose of this SAP is to define the analysis variables and detail the planned analyses to be completed to support the completion of the Clinical Study Report (CSR) for protocol P528-00. Exploratory analyses not necessarily identified in this SAP may be performed to support the PerQseal® clinical programme. Any post-hoc, or unplanned analyses not identified in this SAP, will be clearly identified in the respective CSR.

7. STUDY OBJECTIVES

To confirm safety and performance of the *PerQseal*[®] closure device (DP2-FA1-4) to percutaneously close femoral artery punctures and to induce arterial haemostasis in patients undergoing endovascular procedures requiring an arteriotomy created by 12 to 20 F sheaths. Refer to *Section 4.2*, *Definitions of Terms* for the meaning of haemostasis.

8. STUDY DESIGN

This study will be a prospective, multi-centred, non-randomized study to investigate the safety and performance of the PerQseal® in 75 patients in approximately 10 European investigational sites. The study shall not be blinded prior to, during or post the procedure. All patients undergoing an endovascular procedure requiring an arteriotomy created by 12 to 20 F sheaths, via the common femoral artery will be screened against the inclusion/exclusion criteria.

9. STUDY ENDPOINTS

9.1 Primary Endpoint

Incidence of major vascular access site complications related to the PerQseal[®] closure device up to 1 month from implantation, is no worse than those associated with cut-down and sutured close.

9.2 Secondary Endpoints

Safety: Incidence of minor vascular access site complications directly related to the PerQseal® closure device up to 1 month from implantation.

Performance: assessed by technical success rate for the PerQseal® closure device of the PerQseal® closure device at discharge is no worse than the technical success rates associated with the 'perclose' or 'preclose' technique following EVAR or TAVR.

9.3 Study population

Patients will not be excluded on the basis of age, race, concomitant therapy or co-existing disease. Each centre will continue to enrol eligible patients until a minimum combined Clinical Investigation population of 75 patients is achieved.

Patients with bilateral percutaneous access in the common femoral arteries where both arteries meet all eligibility criteria may, at the discretion of the investigator, both be closed with the PerQseal® closure device. If a PerQseal® is used on the contralateral femoral artery then this will be treated as an independent closure i.e. each limb will be counted as a separate closure only for the purposes of Performance Analysis.

Consented patients who receive contact with the PerQseal[®] closure device become an enrolled subject.

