A one sided confidence interval is appropriate as the study is only interested in the upper bound of the major complication rate. Each complication will be analysed as a separate event.

Completion of 75 patients is recommended, this number of patients should be sufficient to demonstrate non-inferiority whilst allowing for approximately 10% dropout rate.

Subject Cohort: Patients with a femoral arteriotomy created with a 12 - 20 F sheath will be included.

Inclusion criteria:

- Over 18 years of age.
- ii. Subject is willing and able to provide appropriate study-specific informed consent, follow protocol procedures, and comply with follow-up visit compliance.
- iii. Clinically indicated for an endovascular procedure using a common femoral arteriotomy created by a 12 20 F sheath.

Exclusion Criteria:

General Exclusion Criteria:

i. Severe acute non-cardiac systemic disease or terminal illness with a life expectancy of less than six months.

Confidential & proprietary information, not to be reproduced or made available to third parties without prior consent from Vivasure Medical Ltd and not to be used in any unauthorised way.

- ii. Evidence of systemic bacterial or cutaneous infection, including groin infection.
- iii. Known bleeding diathesis, definite or potential coagulopathy, platelet count < 100,000/μl or patients on long term anticoagulants with an INR greater than 1.2 at time of procedure or known type II heparin-induced thrombocytopenia.
- iv. Severe; claudication or peripheral vascular disease (e.g. Rutherford category 3 or greater or ABI < 0.5), documented untreated iliac artery diameter stenosis > 50% or previous bypass surgery/stent placement in the common femoral artery of ipsilateral limb.
- v. Known allergy to any of the materials used in the PerQseal® (refer to Instructions for Use).
- vi. Subject has undergone a percutaneous procedure using a non-absorbable vascular closure device (excluding suture mediated) for haemostasis in the ipsilateral target leg.
- vii. Patients that have undergone a percutaneous procedure in the ipsilateral leg, within the previous 30 days.
- viii. Patients that have undergone a percutaneous procedure using an absorbable intravascular closure device for haemostasis, in the ipsilateral leg, within the previous 90 days.
- ix. Evidence of arterial diameter stenosis > 20% or anterior or circumferential calcification within 20 mm proximal or distal to target arteriotomy site based on pre-procedure CT angiography.

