10. SAMPLE SIZE

The sample size estimate outlined below is based on primary endpoint assessment only for the PerQseal® closure device.

The primary endpoint of safety will be assessed by comparison of the proportion of PerQseal® closure device closures with device related major vascular access site complications up to 1 months (P_{safety}) against a performance goal for safety (PG_{safety}) estimated from literature to be 12.5%.

The minimum sample size to demonstrate non-inferiority of safety against the literature based non-inferiority limit of 0.17 (refer to: Section 11.6 Primary Endpoint Analysis) with a one-sided significance level of 0.025 and study power of 90% is estimated to be 68 closures (assuming a 5% major vascular access site complication rate for the PerQseal® closure device). Refer to the independent statistical report for safety sample size in the CIP Appendix F: Independent Statistical Sample Size Report for Safety for details.

A one sided confidence interval is appropriate as the study is only interested in the upper bound of the major complication rate. Each complication will be analysed as a separate event.

Completion of 75 patients is recommended, this number of patients should be sufficient to demonstrate non-inferiority whilst allowing for approximately 10% dropout rate.

For Performance, in order to claim non-inferiority against technical success rate for 'perclose' or 'preclose' technique the lower bound or a (95%) confidence interval for PerQseal® technical success rate must be shown to be greater than the performance non inferiority limit. In order to achieve this, a minimum sample size of 44 closures is required to demonstrate non-inferiority in a single sample fixed one-sided significance level of 0.025 and power of 0.90 level. The secondary performance endpoint therefore does not drive sample size. The total planned sample size remains at 75 treated subjects.

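### The target of 75 is worded as a floor, as completers and as a total; the primary test needs one number, fixed without regard to events

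*SAP*

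**What the plan says.** Four statements describe the number of patients.

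- SAP 9.3 (Study population): "Each centre will continue to enrol eligible patients until a minimum combined Clinical Investigation population of 75 patients is achieved". No maximum is given.
- SAP 10 (Sample size): "Completion of 75 patients is recommended, this number of patients should be sufficient to demonstrate non-inferiority whilst allowing for approximately 10% dropout rate". The Sample Size part of the protocol synopsis has the same sentence.
- SAP 10, last paragraph: "The total planned sample size remains at 75 treated subjects".
- SAP 8 (Study design): the study is "in 75 patients in approximately 10 European investigational sites".

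Other parts of the plan determine what this number does. Under SAP 9.3, consented patients who have contact with the "closure device become an enrolled subject", so enrolled and treated nearly coincide. SAP 11.1 puts all enrolled subjects into the primary safety analysis. SAP 11.6 compares an exact binomial upper bound with a limit of 0.17. It gives the test level as one-sided 0.025, but it also describes the decision as the upper bound of a one-sided 95% interval. On blinding, SAP 8 says: "The study shall not be blinded prior to, during or post the procedure".

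**The concern.** An exact test of one proportion against a fixed limit allows a whole number of events, and that number rises in steps as n grows. If n is open when the events can be seen, a trial that fails at 75 could be carried to a size at which the same count passes. The stated one-sided 0.025 applies to an n settled without regard to events. A floor without a ceiling does not settle n. Nor does a completion target that, taken literally, implies more enrolled subjects than the stated total.

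**Working it through.** **Inputs.** Limit 0.17, assumed rate 0.05, one-sided 0.025, power 90%, 68 closures, about 10% dropout (SAP 10). Exact method, and the alternative one-sided 95% bound (SAP 11.6). All enrolled subjects analysed (SAP 11.1). Events below are counted per subject, as in SAP 11.6.

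**The plan's 68.** Using the mean of the two variances: (1.960 + 1.282)² × [(0.17 × 0.83 + 0.05 × 0.95)/2] / 0.12² = 68.8. The arcsine formula gives 66.0. Both are close to 68. By exact binomial calculation, power at n = 68 is 87.6%, and 74 is the first n to reach 90%.

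**Dropout.** 68/0.9 = 75.6, so 76 enrolled. In reverse, 75 × 0.9 = 67.5. The 75 is therefore an enrolment number with dropout already in it, to within one patient. Literally 75 completers would need 75/0.9 = 83.3, so 84 enrolled.

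**How n decides the verdict.** The exact upper bound for x events in n is the beta quantile with parameters x + 1 and n − x.

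| Events / n | 97.5% bound | Result at 0.025 | 95% bound | Result at 0.05 |
|---|---|---|---|---|
| 6/75 | 0.166 | pass | 0.152 | pass |
| 7/75 | 0.183 | fail | 0.168 | pass |
| 7/80 | 0.172 | fail | 0.158 | pass |
| 7/81 | 0.16998 | pass | 0.156 | pass |
| 7/84 | 0.164 | pass | 0.151 | pass |
| 8/75 | 0.199 | fail | 0.184 | fail |
| 8/82 | 0.183 | fail | 0.169 | pass |

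**Fixed n.** At a true rate of 0.17, P(X ≤ 6; n = 75) = 0.0204. For every fixed n from 75 to 100 the exact error stays below 0.025; the largest value is 0.02498, at n = 81. With n = 75, power at a 5% rate is 91.9%.

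**Continuing after a fail at 75** (one-sided 0.025, true rate 0.17). P(X = 7; 75) = 0.0256.

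- On to 84, tested once there: 0.0204 + 0.0256 × 0.83⁹ = 0.0204 + 0.0048 = 0.0252.
- On to 81, tested there: 0.0204 + 0.0256 × 0.83⁶ = 0.0204 + 0.0084 = 0.0288.
- Re-tested after every subject up to 100: 0.0388.

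At the one-sided 95% level the same mechanism takes the error from 0.0460 at a fixed 75 to 0.0581 if a failed trial is tested at 82.

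**How often this could arise.** Exactly 7 events at n = 75 followed by none in the next six has probability 3.5% at a true rate of 5%, 8.7% at 8% and 4.8% at 12.5%.

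**The case against.** The best defence is that the plan really has one number. SAP 8 and SAP 10 both give 75 as the size, enrolled and treated nearly coincide, and SAP 9.3 has centres enrol *until* 75 is reached. On that view *minimum* and *completion* are loose wording. Much of this stands. The SAP 10 sentence, read whole, includes dropout in the 75, so a reader who infers that the plan requires 84 enrolled is counting dropout twice. The primary analysis needs no quota of completers either, because SAP 11.10 uses data up to last follow-up.

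A reader might also infer that the plan inflates its type I error. The documents do not support that. No section describes re-testing as enrolment continues, or names 81 or 100 as a stopping point. The optional interim in SAP 11.2 has no stated link to extending enrolment. Being unblinded does not prove that the adjudicated, device-related count is known when enrolment closes, although SAP 11.10 reports no earlier device-related access site complication after discharge, so most of the count could be visible early.

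Finally, the protocol available here is a synopsis, and the sample size report is an appendix to the full plan. A closing rule may exist there. What remains is that the SAP governs the test and neither document, as supplied, closes enrolment at a fixed count.

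**Conclusion.** The point holds as an inconsistency in the sample size that touches the primary test. It does not show that the error rate is broken. One sentence sets only a floor, another calls an enrolment number a completion number, and two others give the same figure as the total. The choice of n can reverse the verdict: 7 events at one-sided 0.025, or 8 at the one-sided 95% bound. A headline that 7 events fail at 75 is true only at the first of these levels.

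The size is modest. Any single n from 75 to 100 respects 0.025. Choosing between 75 and 84 on the results gives 2.5%, essentially nominal. The 2.9% and 3.9% figures assume stopping driven by results, which no section describes, and the 3.9% is a worst case. An innocent overshoot to 79 or 80 lowers power only to 90.0% or 89.5%, which is trivial. The figures assume independent subjects and at most one counted event per subject. The reason to act is that an unblinded single-arm trial judged against a fixed limit should leave no room to choose n after seeing events.

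**What to change.** In SAP 9.3, delete the word *minimum* and state that enrolment closes when the 75th subject is enrolled (device contact, as in 9.3.1), that only subjects already in their procedure at that moment may be added, and that all enrolled subjects enter the primary test. In SAP 10 and the protocol synopsis, replace *completion* of 75 patients by *enrolment* of 75 patients. Naming the enrolled subject also settles the unit, since SAP 10 words the endpoint per closure and SAP 11.6 per subject. A numerical cap is optional; 78, for example, still has 90.5% power at a 5% rate. The two confidence levels in SAP 11.6 should be reconciled, so that the allowed count at 75 is either 6 (one-sided 0.025) or 7 (one-sided 95%).

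The cost is wording in three places and no additional patients. The sponsor gives up the freedom to keep enrolling after 75.

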9.3.1 Subject withdrawal/exclusion

A patient is enrolled in the study by signing an Ethics Committee approved Informed Consent Form; if he/she meets all eligibility criteria (both pre-procedure and during the procedure) and there is intent to close the femoral artery puncture site using the PerQseal® and the PerQseal® closure device contacts the patient¹.

Patients on whom the PerQseal[®] closure device is not used due to failure to meet eligibility criteria/withdrawal of consent are considered not enrolled in the study. Patients not exposed to the PerQseal[®] closure device will not require additional post procedure, pre-discharge or post discharge follow-up assessments and will not be included in safety and performance analyses. For

¹ The PerQSeal® closure device is considered to have contacted the patient if the loading cannula of the PerQSeal® closure device is inserted into the Introducer sheath.

enrolled patients that have received exposure to the PerQseal[®] closure device, but the device was not deployed for reasons other than device failure their data will be included in safety, but not performance analyses and all post procedure, pre-discharge and post discharge follow-up assessments will be performed.

A patient may withdraw from the study at any time if he/she decides to do so. However, all data collected to the time of withdrawal will be recorded in the worksheet, with a note to indicate that the patient has withdrawn their consent to further participate in the study. No further follow-up or data will be recorded for that patient on the worksheet or eCRF. Note that routine management and standard practice of care should continue for the patient without prejudice.

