- xvii. Target puncture site is located in a vascular graft.
- xviii. Target arteriotomy in the profunda femoris or superficial femoral artery or is in common femoral artery, but within 10 mm proximal of the bifurcation of the Superficial Femoral /Profunda Femoris artery.
- xix. PerQseal[®] Introducer-sheath to ipsilateral femoral artery diameter ratio is greater than or equal to 1.05. (For S Introducer vessel lumen diameter of less than 6 mm. For L Introducer vessel lumen diameter of less than 7 mm.)
- xx. Subjects with an acute haematoma of any size, arteriovenous fistula or pseudoaneurysm at the target access site; or angiographic evidence of arterial laceration or dissection within the external iliac or femoral artery before the use of the PerQseal® closure device.

*May not be known until after the patient has given informed consent and the procedure has started. In this event, the PerQseal® should not be used and the patient should be considered excluded from the study and intention to treat analysis.

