11. STATISTICAL METHODS

11.1 Analysis populations

All Enrolled subjects (see Section 9.3 Study Population) will be analysed on an Intent-to-Treat (ITT) basis for the Primary and Secondary Endpoint of Safety.

For avoidance of doubt: The ITT analysis population includes all enrolled subjects who undergo attempted access site closure with Vivasure PerQseal® device (i.e. PerQseal® closure device is attempted to be placed into the vasculature and contacted the patient).

All closures from Enrolled subjects will be analysed on a modified Intent-to-Treat (mITT) basis for the Secondary Endpoint of Performance, excluding enrolled subjects which met an exclusion criteria (documented by a protocol deviation).

For avoidance of doubt: The mITT analysis population includes all closures from enrolled subjects who undergo attempted access site closure with Vivasure PerQseal® device (i.e. PerQseal® closure device is attempted to be placed into the vasculature and contacted the patient), with the exception of devices that were prevented from deploying for reasons listed in the exclusion criteria or due to issues associated with the primary procedure.

A secondary analysis population for the primary safety endpoint will include Per-Protocol (PP) for Primary Safety. The PP is a subset of the ITT analysis population with no major protocol deviations and who experienced the safety endpoint or did not prematurely withdraw from the study prior to being evaluated for the primary safety endpoint.

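### SAP 9.3 and 9.3.1 define enrolment differently, so it is unclear whether a treated but ineligible patient belongs to the ITT set for the primary safety endpoint

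*SAP*

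**What the plan says.** SAP 9.3 sets a contact rule with no eligibility condition: "Consented patients who receive contact with the PerQseal[®] closure device become an enrolled subject".

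SAP 9.3.1 repeats consent and device contact, adds intent to close with the device, and makes enrolment conditional on eligibility: a patient is enrolled "if he/she meets all eligibility criteria (both pre-procedure and during the procedure". Its footnote defines contact as insertion of the loading cannula into the Introducer sheath. The next paragraph names who is not enrolled, and it covers only untreated patients: those on whom the "closure device is not used due to failure to meet eligibility criteria/withdrawal of consent are considered not enrolled in the study".

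SAP 11.1 then sets the safety population: "All Enrolled subjects (see Section 9.3 Study Population) will be analysed on an Intent-to-Treat (ITT) basis for the Primary and Secondary Endpoint of Safety". Its clarifying sentence keeps the same word: "The ITT analysis population includes all enrolled subjects who undergo attempted access site closure".

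The footnote to the procedural exclusion criteria (SAP 9.3.3, also in the protocol synopsis) covers criteria that come to light only after consent, once the procedure has started. It says that the device should not be used and that "the patient should be considered excluded from the study and intention to treat analysis". The synopsis gives no other definition of enrolment.

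**The concern.** Take a consented patient in whom the loading cannula was inserted and who is afterwards judged to have failed a criterion. Under 9.3 this patient is enrolled and in the ITT safety set. Under 9.3.1 the patient is neither. Section 11.1 does not choose, because 9.3.1 is a subsection of the section it cites.

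The study has one arm and no blinding (SAP 8). Several procedural criteria rest on measurement or judgement: vessel diameter, distance to the bifurcation, expected tissue-tract depth. Eligibility can therefore be reconsidered after a complication is known. If 9.3.1 governs, that reconsideration decides who counts in the primary safety analysis.

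**Working it through.** **Step 1. Apply each passage to the treated patient later found ineligible.**

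| Place in SAP | Status of this patient |
|---|---|
| 9.3, contact sentence | Enrolled |
| 9.3.1, enrolment sentence | Not enrolled |
| 9.3.1, list of those not enrolled | Silent: covers only patients on whom the device was not used |
| 9.3.3, footnote | Silent: written for patients in whom the device is not used |
| 11.1, ITT | Follows whichever definition of enrolled applies |
| 11.1, mITT | Assumes enrolled: it removes enrolled subjects who met an exclusion criterion |
| 11.11 and Table 23 | Assumes enrolled: there is a deviation category for failed eligibility |
| Table 5 | Assumes enrolled: it reports the share with full eligibility compliance |
| Table 3 | Assumes enrolled: it has a primary-endpoint row for bleeding diatheses, although known bleeding diathesis is exclusion iii |

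Under the 9.3.1 definition the eligibility part of the mITT rule would have nobody to remove, and eligibility failures could no longer separate the PP set from the ITT set. Most of the plan therefore works only with the contact definition.

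**Step 2. Inputs for the size of the effect.** The limit is 0.13 + 0.04 = 0.17 (SAP 11.6). The one-sided level is 0.025 (SAP 10 and 11.6), the interval is exact binomial (SAP 11.6), and 75 patients are planned (SAP 8, 9.3, 10). The documents give no number of treated ineligible patients and no event counts, so those below are assumptions. Subjects are the unit.

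**Step 3. The plan's own figure, as background.** With 0.17 against 0.05, one-sided 0.025 and 90% power, the arcsine approximation gives n = [(1.960 + 1.282) / (2 arcsin √0.17 − 2 arcsin √0.05)]² = 66.02, rounded up to 67. The plan states 68 closures. The present point does not depend on this figure.

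**Step 4. Exact upper bounds.** For x events in n patients, the bound is the (1 − α) quantile of a Beta(x + 1, n − x) distribution. A pass means a bound below 0.17.

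At α = 0.025:
- 6/75: 0.1660, pass. 7/75: 0.1829, fail. The rule allows at most 6 events in 75.
- From 7/75, drop one ineligible patient with an event: 6/74 gives 0.1682. A fail becomes a pass.
- From 6/75, drop one ineligible patient without an event: 6/74 gives 0.1682, still a pass. Drop two: 6/73 gives 0.1704. A pass becomes a fail.

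SAP 11.6 also words the interval as one-sided 95%. At α = 0.05:
- 7/75: 0.1682, pass. 8/75: 0.1842, fail.
- From 8/75, drop one patient with an event: 7/74 gives 0.1703, still a fail. Drop two with events: 6/73 gives 0.1558, pass.
- From 7/75, drop one event-free patient: 7/74 gives 0.1703. A pass becomes a fail.

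At either level, removing one or two patients near the boundary can reverse the conclusion, in either direction.

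**The case against.** The strongest reply is that no sentence in the SAP removes an exposed patient from safety. Section 9.3.1 declares not enrolled only those in whom the device was not used, and leaves out of the analyses only those not exposed. The eligibility phrase can be read as describing the intended enrolment sequence. Section 11.1 cites Section 9.3 and restates the ITT set by attempted closure and contact, without an eligibility condition. The mITT rule and Tables 3, 5 and 23 fit only that reading. This stands as evidence of intent. It does not settle the matter, because 11.1 still says enrolled and 9.3.1 still makes eligibility a condition of enrolment.

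A reader might also infer that the procedural-exclusion footnote takes treated patients out of ITT. It does not: it addresses patients in whom the device should not be used, and it attaches only to criteria xii to xx.

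The arithmetic is also a chosen case. If the true rate is 5%, exactly 7 events in 75 has probability about 0.047, and one of the seven must then be in an ineligible patient. That objection is fair; the figures show sensitivity near the boundary, not likelihood.

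**Conclusion.** The contradiction is real and it reaches the primary analysis set. The documents support the statement that 9.3.1, read literally together with 11.1, would remove a treated but ineligible patient from the ITT safety analysis. They do not support the stronger statement that the plan does remove such patients, since most of the text points to contact-based enrolment.

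Nor do they support a claim that the complication rate is biased downward. It is plausible that patients treated outside the criteria have more access-site complications, but the documents give no rate for them and no figure for how many to expect. Removal can also make the result less favourable.

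At one-sided 0.025, one removed patient with an event can turn a fail into a pass, and two event-free patients can turn a pass into a fail. This rests on assumed counts at the boundary and a planned size of 75. The point should be settled before any outcome is known.

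**What to change.** 1. In SAP 9.3.1, delete the eligibility condition from the enrolment sentence, so that it matches "closure device become an enrolled subject" in 9.3.
2. In SAP 11.1, state that the ITT safety set is every consented patient in whom the loading cannula entered the Introducer sheath, regardless of any later eligibility finding.
3. State that, within the safety analyses, an eligibility violation that is a major protocol deviation removes a patient only from the PP set. The mITT exclusion for the performance endpoint stays as written.
4. Optionally, add to the footnote in SAP 9.3.3 and the protocol synopsis that it applies where the device was not used.

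The cost is a few sentences and no new data. The reported safety rate may be slightly less favourable.
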